#### **Specific Aims and Hypotheses:**

- Specific Aim 1: To determine the effect of prazosin compared to placebo on HA frequency, HA severity and duration, use of abortive/analgesic medications, and HA-related disability.
  - *Hypothesis 1*: Prazosin will be more effective than placebo in ameliorating the effects of persistent PTHA, specifically: a) prazosin will reduce HA frequency, as compared to placebo; and b) prazosin will reduce HA severity and duration, use of abortive/analgesic medications, and HA-related disability, as compared to placebo (secondary outcome measures).
- Specific Aim 2: To determine the effect of prazosin on sleep disturbance, PTSD symptoms, depressive symptoms, alcohol consumption, global cognitive function, health-related quality of life, and global clinical status (secondary outcome measures).
  - Hypothesis 2a: Prazosin will improve sleep quality, PTSD symptom severity, mood, moderation
    of alcohol consumption, cognitive function, health-related quality of life, and global clinical
    status
  - Hypothesis 2b: Improvement in HA parameters will be associated with improvement in sleep quality, PTSD symptom severity, mood, moderation of alcohol consumption, cognitive function, health-related quality of life, and global clinical status.

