#### **Medication-and other Treatment-Related Considerations:**

- The use of HA rescue or symptom-relieving medications will be allowed during the study. This includes triptans, ergotamines, opioids, simple analgesics (e.g. acetaminophen, aspirin, or non-steroidal anti-inflammatories [NSAIDS], and combination analgesics. Their use will be recorded on the concurrent medication CRF during the Preliminary Screening Period (P1) and throughout the remainder of the study. Randomization of participants will be stratified based on whether their use of HA medications meets ICHD-3 beta criteria for overuse of these medications, as described in section 5.5 below.
- Opioid Medications: Use of opioids for treatment of HA or non-HA-related pain or for any other purpose is allowed during the study. Any opioid use would ideally be excluded due to potential confounding effects on interpretation of response to treatment. However, in this population, particularly in Veterans with chronic pain or undergoing minor orthopedic or dental procedures, opioid use is common. Use of opioids, including frequency and dose, will be recorded on the concurrent medication CRF.
- Cannabis: The use of cannabis in any form is not excluded unless its use meets criteria for Cannabis Use Disorder. All use of cannabis will be documented.
- Other Medications: Participants who are using other medications or treatments on a routine basis must be on a stable dose for at least 4 weeks prior to the Preliminary Screening Period (P1), and

must intend to continue the medication at the same regimen for the duration of the trial unless lack of efficacy, safety, or tolerability dictates otherwise. The following medications and treatments are **not** excluded:

- Psychoactive drugs (for example, anticonvulsants, benzodiazepines, antidepressants, sedative/hypnotics),
- Antihypertensive medications (including beta-blockers, calcium channel blockers, angiotensin converting enzyme [ACE] inhibitors, and angiotensin receptor blockers),
- The use of magnesium in any dose that is prescribed for the purpose of HA prevention or treatment. The incidental use of magnesium in multi-vitamins, laxatives, etc. is permissible but must be documented.
- Hormones (for example, testosterone, estrogen, or progesterone) in any form.
- Onabotulinum toxin A and nerve block injections for the purpose of HA prevention is permissible if the treatment response has been stable during the two most recent treatment cycles.

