Participants who fail screen for a reason that may change (e.g., stabilization of medications or treatment) may resume the screening process following stabilization. Previously collected information will be verified followed by resumption of headache logging for 4 weeks. Participants who screen fail for any reason may be rescreened if the reason for the screen fail has changed.

Randomization: before the Baseline Visit, participants will be randomized 2:1 to prazosin or placebo. Randomization will be stratified based on study site, gender, and whether participants meet the following criteria for medication overuse:

- 1. The regular use of ergotamine, triptans, opioids, or combination analgesics on 10 or more days during the Preliminary Screening Period. The term "combination analgesic" is used for formulations designed to treat migraine HAs that combine drugs of two or more classes, each with an analgesic effect or acting as adjuvants (e.g., Excedrin migraine, which contains aspirin, acetaminophen, and caffeine).
- 2. The regular use of individual "simple analgesics" (acetaminophen, aspirin, and other NSAIDS) on 15 more days during the Preliminary Screening Period.
- 3. The regular use of any combination of ergotamine, triptans, opioids, combination analgesics, and/or simple analgesics on 10 or more days during the Preliminary Screening Period, without over-use of any single drug or class alone.
- 4. Caffeine use of 300 mg or more on four or more days per week during the Preliminary Screening Period.

Titration Period (Baseline Visit and Study Drug Titration): At the Baseline Visit, medications will be reviewed, vital signs (BP and HR) will be checked to ensure absence of orthostatic hypotension, and a urine pregnancy test for women of child-bearing potential will be checked and must be negative. For participants who remain eligible for the study, measures will be performed as listed on the schedule of study visits. We will perform a short measurement of the pupillary light reflex. Participants will look into a device that uses an infrared camera to measure the diameter of the pupil at baseline and in response to very brief flashes of light. The measurements take approximately 30 seconds. Including set up and instructions to the participant, the procedure will take approximately two minutes. Blood (approximately 65 ml) will be collected from VA Puget Sound participants only for measurement of potential biomarkers related to headache

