#### **Description of Study Measures:**

Structured Clinical Interview for DSM-5 (SCID-5):A semi-structured interview guide for making DSM-5 diagnoses. It is administered by a clinician or trained mental health professional that is familiar with the DSM-5 classification and diagnostic criteria.

Combat Experiences Scale (CES): The 18-item Combat Experiences Scale will be used to describe the degree of combat trauma exposure in the study sample. Scores range from 1-18. The Combat Experiences Scale has been utilized in many studies evaluating combat veteran samples and is relevant to any war zone setting from WWII to OIF/OEF/OND.

HA Log: A pre-printed form in a weekly calendar format used for self-report of the following, on a daily basis: HA pain severity (maximum for the day, rated as none [=0], mild [=1], moderate [=2], or severe [=3]), number of hours of mild, moderate or severe pain (to nearest ½ hour), any medications used in an attempt to treat the HA, including the name, amount, and whether it provided relief, , and a space for comments.

Migraine Disability Assessment Scale (MIDAS): A 5-item self-administered questionnaire used to quantify HA-related disability. The MIDAS queries the number of days of missed or substantially reduced activity caused by HA in the preceding 3 months, taking into account three domains: schoolwork/employment, household work or chores, and non-work activities (family, social, and leisure). Responses are summed and coded into one of four grades of disability ranging from little or no

disability to severe disability.

HA Impact Test-Short Form (HIT-6): A 6-item self-administered questionnaire measuring impact on "usual daily activities" including work, school, or social activities, pain intensity, fatigue, and desire to lie down, frustration, and difficulty with concentration in the preceding month. The HIT-6 has shown the ability to discriminate between severity levels and between migraine and other HA diagnoses.

PTSD Checklist (PCL-5): A 20-item self-report measure that assesses the DSM-5 symptoms of PTSD on a scale ranging from 0 ("not at all") to 4 ("Extremely")

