**Statistical Analysis:** We will use summary statistics and graphs (e.g., strip charts, box plots, bar charts, scatter plots) to compare subject demographics at baseline by assigned treatment group (prazosin vs. placebo), and to initially compare outcomes by treatment group. Analyses will follow the intent to treat (ITT) principle. We will use a linear mixed effects model for the analysis of the primary outcome: 4-week frequency of moderate or severe HAs (Hypothesis 1a). We will have 4-week measures at four times during the course of the study: at Baseline, and at three different time points post-randomization (after 4, 8, and 12 weeks of steady-dose study drug). The response (dependent) variable will be 4-week frequency of moderate or severe HAs, and the predictor (explanatory) variables will include treatment group, week and a treatment group by week interaction term, along with the covariates site, gender, baseline age, baseline PSQI, time since onset of PTHAs, and analgesic use. A significant treatment group by week interaction term will indicate a significant difference in change from baseline between treatment groups. Results will include p-values, confidence intervals for change from baseline within each group, the confidence interval for difference in change from baseline between the two groups, and effect sizes.

We will also use linear mixed effects models for the secondary outcomes for Hypothesis 1b, i.e., 4-week average of: HA severity, number of hours of moderate to severe HA, individual HA duration, frequency of migraine days, frequency of non-migraine days, and frequency of use of abortive/analgesic medications (all obtained from the HA log); and for degree of HA-related disability (MIDAS and HIT-6). As for the primary outcome, secondary outcomes obtained from the HA log and the HIT-6 will have observations at four time points during the course of the study: Baseline and after 4, 8, and 12 weeks of steady-dose study drug; MIDAS will have observations at Baseline and week 12. The response (dependent) variable will be the secondary outcome, and the predictor (explanatory) variables will be the same as for the primary outcome.

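### Does the undefined covariate 'analgesic use' let on-study medication into the primary model?

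*Combined protocol and SAP*

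**What the plan says.** Section 5.6 (Statistical Analysis) models the 4-week frequency of moderate or severe headaches at baseline and after 4, 8 and 12 weeks of steady dose. The predictors are treatment, week and treatment by week, "along with the covariates site, gender, baseline age, baseline PSQI, time since onset of PTHAs, and analgesic use". The interaction is the test of interest, and the analysis follows intention to treat. The secondary models reuse these predictors, except that baseline PSQI is dropped where sleep is the outcome. One secondary outcome is how often abortive or analgesic medication is used.

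Three other places bear on the term:

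- **Section 5.5, Randomization.** "Randomization will be stratified based on study site, gender, and whether participants meet the following criteria for medication overuse". The four criteria all refer to the Preliminary Screening Period. One of them is not about analgesics: "Caffeine use of 300 mg or more on four or more days per week during the Preliminary Screening Period".
- **Section 5.4, medication considerations.** On headache rescue medication: "Their use will be recorded on the concurrent medication CRF during the Preliminary Screening Period (P1) and throughout the remainder of the study". The next sentence says randomisation is stratified on overuse of these medications. On opioids: "Use of opioids for treatment of HA or non-HA-related pain or for any other purpose is allowed during the study", followed by "Any opioid use would ideally be excluded due to potential confounding effects on interpretation of response to treatment".
- **Section 5.5, HA Log.** The daily log captures "any medications used in an attempt to treat the HA, including the name, amount, and whether it provided relief".

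**The concern.** The covariate could be read in several ways: the yes/no overuse stratum, analgesic days in screening, or analgesic days in each 4-week window on treatment. Their scope differs too. The log covers medication taken for headache, the concurrent medication form also covers opioids taken for other reasons, and caffeine alone can put someone in the stratum. Age and PSQI are marked as baseline values in the same list; this term is not. On-study use is recorded, so a time-varying covariate is feasible. The opioid remark in Section 5.4 could be taken as a motive for adjusting for it.

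That reading would do harm. Hypothesis 1b in Section 3.0 expects prazosin to lower abortive and analgesic use. Adjusting for on-study use would remove part of the treatment effect from the primary test. Under the rule that secondary models share the same predictors, it would also put analgesic use on both sides of its own model.

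**Working it through.** **1. The plan's own figure.** Inputs from Section 5.6: 74 and 37 completers, effect size 0.57, two-sided 5%. The noncentrality is 0.57 / √(1/74 + 1/37) = 0.57 / 0.2013 = 2.83. With 109 degrees of freedom the power is 80.1%, against 80% stated. Dropout of 30% gives 111 / 0.7 = 158.6, against 160 randomised. The covariate plays no part in these figures.

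**2. The covariate list set against the design.**

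| Covariate | Fixed before randomisation? | Stratification factor? |
|---|---|---|
| Site | yes | yes |
| Gender | yes | yes |
| Baseline age | yes | no |
| Baseline PSQI | yes | no |
| Time since onset of headaches | yes, though not labelled baseline | no |
| Analgesic use | not stated | third factor is medication overuse |

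Two of the three stratification factors are named. The third concerns headache-medication use, and this is the only entry that could stand for it. The missing baseline label proves little, because time since onset has none either.

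**3. Pre-randomisation readings.** The covariates are listed as main effects, with no interaction with week. A value that is constant within a person shifts all four occasions equally. It therefore drops out of a within-person change when the data are complete. With 111 completers and no dropout, no covariate, the stratum and baseline analgesic days give identical estimates and standard errors.

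Dropout was examined by simulation: 107 and 53 randomised, 30% lost completely at random, a random-intercept model, 1,000 replicates per case. The true effect was 3 days (0.57 × 5.3 = 3.02, taking an SD inside the plan's range of 5 to 6). A stratum prevalence of 40% and a stratum effect of 3 days were assumed. All three options gave -2.97 to -3.01 days, standard error 1.01 to 1.02 and power 83 to 85%.

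**4. On-study reading, for scale only.** Adjusted effect = 3 - b × d. Here d is the treatment difference in analgesic days, and Section 5.6 cites about 1 and 2.7. The slope b of headache days on analgesic days is assumed, with no source in the documents.

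| d | b | 3 - b × d | Simulated estimate | Simulated power |
|---|---|---|---|---|
| 1 | 0.2 | 2.80 | -2.74 | 78.2% |
| 1 | 0.6 | 2.40 | -2.36 | 80.0% |
| 2.7 | 0.2 | 2.46 | -2.30 | 63.0% |
| 2.7 | 0.6 | 1.38 | -1.26 | 34.4% |

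The simulated estimates lie 0.04 to 0.16 day nearer zero than the formula, and that gap is unexplained. The table shows a direction and a rough size, not a precise loss.

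**5. The analgesic-use model.** With b = 0.2, adding baseline analgesic days moves the estimate from -1.02 to -1.01 (d = 1) and leaves it at -2.65 (d = 2.7). The reported standard error goes from 0.957 to 0.926 and from 1.033 to 1.000, about 3% smaller in each case. The empirical spread does not improve (0.957 to 0.972 and 0.997 to 1.003). The effect is trivial.

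**The case for a change.** The strongest case for a change is that this is the only covariate in the list that is also a trial outcome, that on-study values are collected, and that the text does not exclude them. Section 5.7 breaks the blind for each participant at completion or discontinuation, so a term left open could be settled with treatment arms known. A sentence would cost little.

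Part of this stands. The definition is missing, and 'analgesic use' is a loose label for a stratum that caffeine alone can satisfy. Late choice is a fair worry in general, but here the pre-randomisation candidates give almost the same answer, so choosing among them gains nothing. If screening analgesic days were used instead and the overuse stratum left out, step 3 shows the treatment-by-week estimate would still hold.

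The rest does not stand. The opioid remark in Section 5.4 concerns opioids only, explains a decision about permitted medication, and says nothing about the model. It cannot show that on-study values must be ruled out, since calling something a confounder normally argues for adjusting for it. The sound reason against on-study adjustment is that such use follows randomisation and is expected to respond to treatment. The plan's intention-to-treat statement and its listing of analgesic use as an outcome already lead an analyst there. Taken literally, the on-study reading makes the analgesic-use model regress a variable on itself, which no analyst would leave in place.

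The PSQI exception has no counterpart for analgesic use, but step 5 shows that a baseline term in that model is harmless.

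**Conclusion.** No change to the plan is needed. The gap is real but is a matter of detail. The list, the stratification and Section 5.4 point to a value fixed before randomisation, most naturally the overuse stratum, and nothing in the documents proposes an on-study covariate. On the pre-randomisation reading the treatment-by-week result is the same with or without the term: identical with complete data, and within 0.04 day across the simulated cases with 30% dropout. This rests on the covariate entering as a main effect, as listed, and on dropout completely at random in the simulation.

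The attenuation to between 2.80 and 1.38 days, and power as low as 34%, apply only under a reading the documents do not support and an assumed slope. They are not a harm present in the plan. Naming the stratum when the analysis is programmed would be ordinary good practice.

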#### 5.6 Data Analysis

**Sample Size:** Our estimate of required sample size for the primary outcome is based on previous studies of chronic migraine HA, which reported standard deviations for change from baseline at 16 weeks in number of migraine days/month on the order of 5-6 days for both placebo and active drug groups, and a difference in change from baseline at 16 weeks in mean number of chronic migraine HA days/month between treatment groups of about 4 days (i.e., an effect size of about 0.67). An inclusion criterion for these studies was a minimum of 15 HA days/month, whereas the corresponding inclusion criterion for our proposed study is a minimum of 8 HA days/month. We therefore may see a smaller effect size. A trial with 111 completers (74 in the prazosin group, and 37 in the placebo group) yields 80% power to detect an effect size of 0.57 for a difference in change from baseline based on a standard two-sample t-test using a two-sided 5% Type I error level. Because we will be using linear mixed effects models to analyze this outcome, our power should be greater than 80% to detect an effect size of 0.57.

To arrive at the required number of participants to randomize, we are assuming a 30% dropout rate during the Titration and Steady-Dose Periods, based on the experience of Study Consultant [name] in other HA trials in the active-duty SM population. This dropout rate is due mainly to service-related events, such as reassignment or deployment, rather than to adverse drug effects. With a 30% dropout rate, we will need to randomize 160 participants who have met all eligibility criteria. Conservatively assuming a screen-fail rate of approximately 30% based on the Pre-Treatment Screening (e.g., meeting inclusion criteria for HA frequency/severity, adequate compliance with log keeping, voluntary study withdrawal, etc.), 228 potential participants will need to be recruited and enrolled to provide sufficient participants randomized for completion of the study.

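### The covariates carry no week interaction, so the treatment-by-week test is in effect not adjusted for the factors used to randomise

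*Combined protocol and SAP*

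**What the plan says.** Section 5.6 (Statistical Analysis) makes the 4-week headache frequency the response at four times: baseline, and after 4, 8 and 12 weeks at steady dose. The predictors are treatment, week and treatment by week, "along with the covariates site, gender, baseline age, baseline PSQI, time since onset of PTHAs, and analgesic use". Treatment by week is the only interaction listed, and its significance is read as a difference between arms in change from baseline. The secondary models for Hypotheses 1b and 2a take over the same predictors, except that baseline PSQI is dropped for sleep outcomes.

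Section 5.5 (Randomization) states: "Randomization will be stratified based on study site, gender, and whether participants meet the following criteria for medication overuse". Site and gender reappear in the model. Overuse does not appear by name. The nearest term is analgesic use, which has no definition and no stated timing. One of the four overuse criteria concerns caffeine, so analgesic use read literally is not the stratum.

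Section 5.6 (Sample Size) rests on an unadjusted comparison. It counts on 74 prazosin and 37 placebo completers, 111 in all, and says that this number "yields 80% power to detect an effect size of 0.57". The calculation is "based on a standard two-sample t-test", two-sided at 5%. It then says: "Because we will be using linear mixed effects models to analyze this outcome, our power should be greater than 80" per cent.

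**The concern.** A reader of section 5.6 would take the primary result to be adjusted for six covariates, among them two of the three stratification factors. Because baseline is itself a response, a main effect moves a participant's baseline and follow-up values by the same amount. It therefore explains differences in level between participants, not differences in change, and the test concerns change.

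Two things are at stake. First, if site, gender or overuse predict change, the standard error is larger than it need be, and the design's stratification is not carried into the analysis. Second, section 5.6 expects 30% dropout, mainly from reassignment or deployment, and section 5.2 has active-duty members seen at one of the two sites. Dropout related to site is foreseeable, and main effects handle it only in part if change also differs by site.

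**Working it through.** **1. The plan's own figure.** Inputs from section 5.6: 74 and 37 completers, effect size 0.57, two-sided 5%, t-test. The noncentrality is 0.57 / √(1/37 + 1/74) = 0.57 / 0.2013 = 2.831. With 109 degrees of freedom and critical value 1.982, power is 80.1%. The stated 80% is reproduced. It assumes no covariates.

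**2. Why main effects cancel.** Let y_it be the response of participant i at time t, with arm-by-time means m_at and a time-constant covariate vector x_i:

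y_it = m_at + x_i′β + e_it

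With complete data and a common covariance, the generalised least squares solution is m̂_at = ȳ_at − x̄_a′β̂. The term x̄_a′β̂ does not depend on t. So m̂_at − m̂_a0 = ȳ_at − ȳ_a0 for any β̂, and the treatment-by-week estimate is the raw difference in mean change.

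**3. Numerical check, complete data (74 and 37, simulated).** Under compound symmetry and under an unstructured covariance, adding six main effects changed the week-12 contrast by zero in every data set. In a REML random-intercept example:

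| Covariates | Estimate (days) | SE |
|---|---|---|
| None | −1.44261 | 1.14917 |
| Main effects | −1.44261 | 1.14917 |
| Crossed with week | −1.27926 | 1.12589 |
| Main effects plus time-varying analgesic use | −0.40416 | 0.70404 |

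**4. With 30% dropout (160 randomised).** Observed covariate means now differ between time points, so cancellation is no longer exact. In 81 REML runs, assuming the covariates explain 20% of the variance of change, main effects moved the estimate by 0.14 days on average (maximum 0.54). The mean model SE was 1.123 with no covariates, 1.118 with main effects (0.4% lower) and 1.082 with covariate-by-week terms. The empirical SDs were 1.135, 1.105 and 0.999, and are rough at 81 runs.

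When dropout was made to depend on the covariates in opposite directions in the two arms (300 runs), the mean error in days was:

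| Covariates affect | None | Main effects | Crossed with week |
|---|---|---|---|
| Level only | −0.32 | +0.06 | +0.05 |
| Level and change | −0.85 | −0.30 | +0.02 |

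For scale, section 5.6 puts the SD of change "on the order of 5-6 days for both placebo and active drug groups", so the effect size of 0.57 is 0.57 × 5 = 2.85 to 0.57 × 6 = 3.42 days.

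**5. Power after crossing.** The noncentrality becomes 2.831 / √((1 − R²)·f) with 109 − q degrees of freedom. R² is the share of the variance of change explained (assumed). q is the number of covariates, and f is the expected cost of chance imbalance: f = 1 if the factors are balanced, otherwise f = 1 + q/(108 − q).

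| Crossed terms | R² = 0 | 5% | 10% | 20% |
|---|---|---|---|---|
| Three factors, balanced (f = 1) | 80.1% | 82.1% | 84.1% | 88.0% |
| Three, unbalanced (f = 1 + 3/105 = 1.029) | 79.0% | 81.0% | 83.0% | 87.1% |
| Six, unbalanced (f = 1 + 6/102 = 1.059) | 77.8% | 79.9% | 81.9% | 86.2% |

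For six covariates the variance breaks even at R² = 1 − 1/1.059, about 5.6%. For three unbalanced ones it does so at 1 − 1/1.029, about 2.8%.

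**The case against.** The strongest reply is that this is an optional precision choice of uncertain sign. Randomisation keeps the unadjusted contrast valid, stratification already limits imbalance in the three factors, and putting baseline in the response removes their effect on level. The documents give no R² for change, and crossing all six covariates would lower power if R² is small. All of this stands, and it limits the request to the three randomisation factors. Stratification makes those nearly free, although dropout may disturb their balance and move power towards the second row of the table.

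Stronger readings that a reader might infer are not supported:

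- **That the covariates do nothing in this trial.** This is exact only for complete, time-constant covariates. With 30% dropout they add little precision, but in the simulations they removed part of the bias. Section 5.6 also plans to compare dropout between arms and to consider multiple imputation.
- **That the test is invalid or the trial underpowered.** The 80% comes from an unadjusted t-test and is unaffected.
- **That the expectation of power above 80% is contradicted.** Section 5.6 credits that to the mixed model, not to the covariates, and the model also uses partial data from participants who drop out.
- **That all randomisation factors are in the model as main effects.** This is clear only for site and gender.

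Two points depend on wording. Section 5.6 does not say that its list of predictors is exhaustive, so main effects only is the natural reading rather than a stated rule. The coding of week is not given either. With linear week the test would concern a difference in slopes. On complete data each arm's intercept would still absorb the main effects, but the contrast would no longer be the raw difference in mean change.

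**Conclusion.** The point holds in a limited form. On the natural reading, the primary comparison is in effect unadjusted for site, gender and medication overuse: exactly so with complete data, and very nearly so for precision under the planned dropout. Overuse is not clearly in the model at all. The test and the stated 80% power remain sound.

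For three balanced factors, the power forgone is about 2, 4 or 8 percentage points if they explain 5%, 10% or 20% of the variance of change, and essentially none if they explain nothing. Bias arises only if dropout depends on the factors differently by arm. In one assumed scenario, main effects left −0.30 of a −0.85 day error. The R² values, covariance parameters and dropout patterns are assumptions, and the simulations are small (81 to 300 runs).

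The undefined analgesic use needs settling in the same sentence. If it varies over time it is not inert: it moved the contrast from −1.44 to −0.40 days in the example, and it would adjust for a variable that is itself a secondary outcome.

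**What to change.** In section 5.6, for the primary and secondary models:

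- Enter site, gender and the baseline medication-overuse stratum each with a factor-by-post-baseline term, or a factor-by-week term.
- Define analgesic use as that baseline stratum, as classified at randomisation, and not as a time-varying value.
- State that week is categorical, if that is intended, and whether the remaining covariates stay as main effects.

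The cost is a change of wording and about three extra parameters with a post-baseline indicator, or nine (three factors × three post-baseline times) with full week interactions. No new data are needed. Crossing all six covariates is optional, since it lowers power unless they explain more than about 5.6% of the variance of change.

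### Baseline headache frequency is modelled as an outcome but not adjusted for; adjusting is a free gain of about 4-7 points of week-12 power with equal SDs, and 0.5-3 points if the baseline SD is 0.8 of follow-up

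*Combined protocol and SAP*

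**What the plan says.** All references are to the combined protocol and SAP.

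- **Response.** Section 5.6 (Statistical Analysis) takes 4-week frequency of moderate or severe headaches as the response in a linear mixed model: "We will have 4-week measures at four times during the course of the study: at Baseline, and at three different time points post-randomization". These follow 4, 8 and 12 weeks of steady dose.
- **Predictors.** Group, week and their interaction, "along with the covariates site, gender, baseline age, baseline PSQI, time since onset of PTHAs, and analgesic use". Baseline PSQI is listed and baseline headache frequency is not. Nothing constrains the arms to share a baseline mean.
- **Decision sentence.** "A significant treatment group by week interaction term will indicate a significant difference in change from baseline between treatment groups". The plan also promises "the confidence interval for difference in change from baseline between the two groups". Neither statement names a visit, and the coding of week is not given.
- **Sizing.** Section 5.6 (Sample Size) has 74 and 37 completers, which "yields 80% power to detect an effect size of 0.57 for a difference in change from baseline based on a standard two-sample t-test"; it adds that with the mixed model "our power should be greater than 80% to detect an effect size of 0.57". For dropout, "we are assuming a 30% dropout rate during the Titration and Steady-Dose Periods", giving 160 randomised.
- **Strata.** Section 5.5 (Randomization) stratifies by site, gender and medication overuse; the overuse criteria include a caffeine criterion.

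**The concern.** When baseline is a response row with its own group effect, the group-by-week contrast at a visit subtracts the whole baseline difference between arms. That is a change-score comparison. Regression on baseline subtracts only the part of the difference that predicts follow-up, so it normally leaves less residual variance. The trial collects a 4-week baseline log on every randomised participant and then does not use it in this way. The trial also expects to lose 30% after randomisation and says that its effect may be smaller than in the studies it cites, so precision has value.

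There are two smaller gaps in the same paragraph. The overuse stratum used in randomisation does not appear in the model as such; an undefined analgesic-use covariate stands where it would be expected. And a reader has to infer which contrast decides the primary question.

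**Working it through.** **1. The plan's own figure.** Noncentrality is 0.57 / √(1/74 + 1/37) = 2.83. With 109 degrees of freedom and two-sided 5%, power is 80.1%. The stated 80% reproduces.

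**2. Variance ratio, complete data.** Set the follow-up SD to 1, let k be baseline SD / follow-up SD, and let r be the baseline-to-follow-up correlation.

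- Variance of change: 1 + k² − 2kr
- Variance after adjustment: 1 − r²
- Ratio: (1 − r²) / (1 + k² − 2kr)

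The documents give no r for headache frequency. I assume 0.5-0.7; the only ICCs reported, in the Sample Size text, are 0.6 and 0.7, for other scales. I show k = 1 and k = 0.8. The 8-day entry minimum could narrow the baseline SD, but it also counts treated headaches of any severity, which the primary outcome does not, so its effect on k is unknown.

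| k | r | Ratio | Completer power, unadjusted | Adjusted |
|---|---|---|---|---|
| 1 | 0.5 | 0.75/1.00 = 0.750 | 80.1% | 90.0% |
| 1 | 0.6 | 0.64/0.80 = 0.800 | 80.1% | 88.0% |
| 1 | 0.7 | 0.51/0.60 = 0.850 | 80.1% | 86.1% |
| 0.8 | 0.5 | 0.75/0.84 = 0.893 | 80.1% | 84.4% |
| 0.8 | 0.6 | 0.64/0.68 = 0.941 | 80.1% | 82.4% |
| 0.8 | 0.7 | 0.51/0.52 = 0.981 | 80.1% | 80.9% |

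Adjusted power divides the noncentrality by the square root of the ratio. At k = r the ratio is 1 and the gain is zero.

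**3. All randomised.** The planned model uses everyone with data, so the fair comparison is on 107/53 with 30% lost by week 12. I took the generalised least squares variance of the week-12 difference in change under the planned model and under a common baseline mean, with equal correlation between all visits and 120 degrees of freedom. Four dropout patterns were used (percent lost before week 4, between weeks 4 and 8, and between weeks 8 and 12): 30/0/0, 10/10/10, 15/10/5 and 0/0/30. Ranges are across patterns.

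| k | r | Planned | Adjusted | Gain, points |
|---|---|---|---|---|
| 1 | 0.5 | 83.4-84.8% | 90.2-91.6% | about 7 |
| 1 | 0.6 | 82.8-84.7% | 88.3-90.1% | about 5.5 |
| 1 | 0.7 | 82.2-84.6% | 86.3-88.7% | about 4 |
| 0.8 | 0.5 | 81.7-83.4% | 84.6-86.4% | about 3 |
| 0.8 | 0.6 | 81.1-83.4% | 82.7-85.0% | about 1.6 |
| 0.8 | 0.7 | 80.6-83.4% | 81.2-83.9% | about 0.5 |

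Fitting both models to simulated trials (pattern 10/10/10, k = 1) gave 85.2% against 91.4% at r = 0.5, and 84.4% against 87.8% at r = 0.7.

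**4. In days.** The sizing cites trials "which reported standard deviations for change from baseline at 16 weeks in number of migraine days/month on the order of 5-6 days". For completers, the effect detectable with 80% power is 0.569 SD unadjusted, or about 2.85-3.4 days. Adjusted it is 0.493-0.525 SD (2.5-3.15 days) at k = 1 and 0.538-0.564 SD (2.7-3.4 days) at k = 0.8.

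**5. The SDs that the documents do give.** Table 1 (Preliminary Studies, n = 74) has headache frequency with SE 0.94 before and 0.34 after treatment. The SDs are 0.94 × √74 = 8.1 and 0.34 × √74 = 2.9, so k is about 2.8. The ratio in step 2 would then be about 0.11-0.13 for r = 0.5-0.7, a much larger gain. I do not rely on it: the series was open-label and uncontrolled, and its mean fell from 12.40 to 4.77 per month, so the ratio may not carry over.

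**6. Other readings of the interaction term.** Same all-randomised basis, planned model, k = 1, r = 0.5-0.7:

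| Test | Benefit sustained from week 4 | Benefit builds linearly |
|---|---|---|
| Joint 3-df | 86-94% | 71-77% |
| Linear-week slope | 80-89% | 86-90% |

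**The case against.** The strongest reply is that nothing here is wrong. The trial is sized on change from baseline and analysed on difference in change, so design and analysis agree. Type I error is not at risk, and the planned week-12 contrast has 81-85% power under every assumption in step 3. All of that stands. A reader might infer that the planned analysis is biased, ignores baseline altogether or is underpowered; the documents support none of these. Baseline is subtracted, only less efficiently than it could be.

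Second, the gain can be trivial: half a point at k = 0.8 and r = 0.7, and nothing at k = r. That is true. Adjustment is safe in that case because, given a common baseline slope in both arms, it costs only about one degree of freedom. The condition matters. With slopes of 1.1 on placebo and 0.7 on prazosin, the pooled slope is (74 × 0.7 + 37 × 1.1)/111 = 0.83. The slope mismatch then adds 0.018/74 + 0.071/37 = 0.0022 baseline variances, against 0.090/74 + 0.010/37 = 0.0015 for the change score. This is an edge case, but it rules out an unqualified claim that adjustment never loses.

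Third, a reader might infer that the unnamed contrast undermines the power claim. Mostly it does not. The change-score sizing, the 12-week PSQI power target and the single promised confidence interval all point to one week-12 difference. Of the alternatives in step 6, only the joint test under a linearly building effect falls below 80%.

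Fourth, analgesic use may be meant as shorthand for the overuse stratum. It may, but the plan does not say so, and the stratum also counts caffeine. No power figure is attached to this point.

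**Conclusion.** The point holds as a loss of efficiency that costs nothing to recover; it should be fixed, but it does not threaten validity. On all randomised, week-12 power rises from about 82-85% to 86-92% with equal SDs, and from about 81-83% to 81-86% with the baseline SD at 0.8 of follow-up. These figures rest on an assumed correlation of 0.5-0.7, the two assumed SD ratios, 30% dropout by week 12 with baseline kept for everyone, and an effect of 0.57 SD of change. The true gain could be near zero, or larger if the SD ratio is nearer to that in Table 1. The plan's claim of more than 80% power is met at week 12. The unnamed contrast is a gap in specification that belongs in the same edit; it does not carry the point.

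**What to change.** In section 5.6:

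- Model the three post-baseline 4-week frequencies with baseline 4-week frequency as a covariate, or keep four rows and constrain the arms to a common baseline mean. Use categorical week, treatment and treatment-by-week.
- Include the randomised strata (site, gender and medication overuse as defined in section 5.5), with overuse replacing the undefined analgesic-use covariate. Keep age, baseline PSQI and time since onset.
- Replace the interaction sentence with one named 1-df contrast: the adjusted difference between arms at Steady-Dose week 12, which matches the sizing.
- Restate power for that contrast, with the correlation and SD ratio assumed.

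The cost is SAP wording and a few degrees of freedom, settled before any comparison of outcomes by arm. No new data are needed: the baseline log, the strata and the covariates are already collected.
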